7.3 Efficacy Assessments

Disease assessments will occur as per SoE (Table 1) until progression.

Screening (Baseline) imaging must be performed within 4 weeks prior to C1D1.

During the treatment period, imaging will be performed 6 weeks and 12 weeks after C1D1, then every 9 weeks until EOT. Week 6 imaging should be performed within 1 week prior to C3D1 and Week 12 imaging should be performed within 1 week prior to C5D1. All other imaging should be performed within ±2 weeks of the scheduled time point. Disease assessments should take place at the timepoints specified even if study drug dosing is delayed.

During the follow-up period, patients who discontinued study drug for reasons other than disease progression or initiation of other anti-cancer therapy will have imaging performed every 12 (± 2) weeks until 1 year from EOT, then every 6 months until disease progression, up to 3 years from EOT; when patients discontinue the study drug because they are planned to undergo a HSCT or to receive CAR-T therapy, imaging will continue the same way. Moreover, HSCT information such as but not limited to type of HSCT, conditioning therapy

should be recorded in the eCRF. Likewise for CAR-T therapy, the type of CAR-T used including conditioning therapy should be recorded in the eCRF.

If a scan has been performed within 6 weeks of EOT, it does not need to be repeated at EOT.

Additional disease assessments may be obtained, if clinically indicated.

Positron emission tomography-computed tomography (PET-CT) of the neck/chest/abdomen/pelvis and other areas of known disease or newly suspected disease, as well as a clinical examination for lymphoma, will be performed. If it is known that the tumor is tracer-avid, the baseline CT as part of the PET-CT does not have to be performed with contrast medium; however, if the tumor is not tracer-avid, diagnostic CT should be used and contrast medium considered, however patients who have a contraindication to CT IV contrast medium should have MRI examinations performed instead. The assessment method determined to identify sites of disease at Baseline (i.e., PET-CT, CT, MRI) should be used for all subsequent assessments.

Patients whose tumor is not PET-avid should have a bone marrow biopsy as part of their baseline staging and disease assessment if clinically appropriate.

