9.7.1 Overall Response Rate

The ORR will be defined as the proportion of patients with a best overall response (BOR) of CR or PR. The overall response category will be derived based on response assessment performed on or before the start of subsequent anti-cancer therapy. For the primary ORR analysis in the all-treated population, patients with a CR or PR will be counted as successes and all other patients (including those with missing response information) will be counted as failures.

The percentage of ORR with its 95% confidence interval (CI) will be presented. In contrast to CR, PR, or PD, a BOR of SD can only be made after the patient is on-study for a minimum of 35 days after the first dose of study drug. Any tumor assessment indicating SD before this time period will be considered as a non-evaluable for BOR if no assessment after this time period is available.

9.7.2 **Duration of Response**

The DOR will be defined among responders (CR or PR) as the time from the earliest date of first response until the first date of either disease progression or death due to any cause. The date of disease progression will be defined as the earliest date of disease progression based on central review. For patients who have not progressed or died at the time of the analysis, censoring will be performed using the date of the last valid disease assessment prior to

initiation of a new anticancer therapy (including HSCT). A sensitivity analysis of DOR is planned to be conducted in which the DOR for patients undergoing SCT is not censored at the last evaluable disease assessment prior to SCT. The data will be analyzed by the Kaplan-Meier method. The median DOR and 95% CI will be presented. DOR will be analyzed by response subgroup (CR, PR). Further details will be outlined in the SAP.

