4.9 Efficacy Analyses

Disease assessment will be performed according to protocol. The endpoints described in this section, if not mentioned specifically, use the independent reviewer's evaluation according to the 2014 Lugano Classification criteria before the start of subsequent anticancer therapy or procedure.

Tumor assessment data (target lesions, non-target lesions, new lesions, overall response, SUV max, Deauville score, etc.) will be listed. A separate listing will contain derived data for duration of response (DOR), relapse-free survival (RFS), progression-free survival (PFS), and Overall survival (OS).

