4.9.1 Overall Response Rate

Overall response rate is defined as the proportion of patients who achieve either CR or PR as best overall response (BOR) as determined by central review according to the 2014 Lugano Classification criteria before the start of subsequent anticancer therapy or procedure. For the primary ORR analysis in the all-treated population, patients with a CR or PR will be counted as successes and all other patients (including those with missing response information) will be counted as failures.

The order of overall response category is: CR, PR, SD, NE, PD (including disease recurrence/ relapse). The overall response category will be derived based on response assessment performed on or before the start of subsequent anticancer therapy/procedure. Patients without documented subsequent anticancer therapy and/or with missing start date of anticancer therapy will be considered as not having received subsequent anticancer therapy. A BOR of SD can only be made after the patient is on-study for a minimum of 35 days after the first dose of study drug. Any tumor assessment indicating SD before this time period will be considered as NE for BOR if no assessment after this time period is available.

The overall response rate and the corresponding 95% two-sided exact CI will be presented. Subgroup analysis may be provided for disease subtype, disease stage, age group, sex, country, response to the first line and/or most recent line of prior systematic therapy (relapse: CR+PR vs. refractory: SD+PD vs. other: NE + missing), and other relevant variables.

Percent change from baseline in the sum of product of the perpendicular diameters (SPD) for target lesions will be presented for available data in the all-treated population. These data will also be displayed as a waterfall plot, with vertical bars representing the sorted values of best percent reduction for each patient.

A sensitivity analysis of ORR determined by the independent reviewer's evaluation will be conducted for the per-protocol population if relevant.

A sensitivity analysis of ORR will be conducted in which best overall response is determined by investigators.

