8.1 General conventions

8.1.1 Missing data

Handling of missing/partial dates

In general, imputation of missing dates will be made for AE onset date, AE resolution date, date of death, medication start/end dates, start and end dates of prior and subsequent therapies, and date of initial diagnosis for reporting. No imputation should be done at the data level.

- If dates are completely missing, no imputation will be made.
- For any partial date with missing year, no imputation will be made.
- For missing initial diagnosis date, if only day is missing, then the 1st of the month will be used; if only year is present, then Jan 1st will be used. If such imputed date for initial diagnosis is on or after date of first dose, then date of first dose - 1 will be used.
- If the imputed date is for an AE start date and is in the same year and month as but before the first dose date, then the first dose date will be used, or if the imputed AE start date is after the AE end date, then the AE end date will be used. If the imputed date is for an AE start date and is in the same year and month as but after the last dose date + 30 days, then the last dose date + 30 days will be used.
- If a medication date or time is missing or partially missing, so it cannot be determined whether it was taken prior or concomitantly, it will be considered as a prior and concomitant medication.
- If the imputed date is for a date of death and is before the last date that the patient is known to be alive, the latter date will be used.
- If the date part is missing for new anticancer therapy, the month and year will be used for comparison with disease assessment.

Handling of missing relationship to investigational product of TEAEs

If the assessment of the relationship to IP is missing, then the relationship to IP has to be assumed and the TEAE considered as such in the frequency tables of possibly related TEAEs, but no imputation should be done at the data level.

No other imputation of values for missing data will be performed.

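### SAP 4.9.1 treats subsequent therapy with no start date as not given; where no related record is dated, a response first read after that therapy can count in ORR or the CR rate.

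*SAP*

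**What the plan says.** **The window.** Protocol 9.7.1: "The overall response category will be derived based on response assessment performed on or before the start of subsequent anti-cancer therapy". SAP 4.9 applies the same limit to its efficacy endpoints generally, using assessments "before the start of subsequent anticancer therapy or procedure", and SAP 4.9.1 repeats it for BOR.

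**The missing-date rule.** The next sentence of SAP 4.9.1 covers two groups joined by and/or: patients with no documented subsequent therapy, and patients "with missing start date of anticancer therapy will be considered as not having received subsequent anticancer therapy". A missing date is therefore enough on its own, even when the therapy is documented.

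**Date handling in SAP 8.1.1.** Three lines bear on this:
- "If dates are completely missing, no imputation will be made"
- "For any partial date with missing year, no imputation will be made"
- "If the date part is missing for new anticancer therapy, the month and year will be used for comparison with disease assessment"

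**Imaging after later therapy.** Protocol 7.3 and the Schedule of Events stop follow-up imaging at progression or at other anticancer therapy, with an exception for transplant and CAR-T. When patients stop study drug because "they are planned to undergo a HSCT or to receive CAR-T therapy, imaging will continue the same way".

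**The count that decides the trial.** ORR is tested by an exact binomial test against 35% (SAP 3.1; protocol 9.4, Table 7). Under SAP 4.9.3 the CR rate is the share of patients with a BOR of CR, so it inherits the same window. SAP 3.3 lists no modification to the protocol's statistical section.

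**The concern.** The window keeps the next therapy's effect out of the response count. The missing-date clause removes that protection exactly where it is needed: for a patient known to have had another treatment at an unknown time. Without a cut-off, every later scan stays eligible.

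BOR takes the best category, so extra scans can add a response but never remove one. The error therefore runs only in the anti-conservative direction, in a single-arm trial decided by a responder count. Other missing-data rules in the SAP lean the opposite way. A missing response counts as failure (4.9.1), an AE of uncertain onset is classed as treatment-emergent (4.8.1.1), and a missing causality assessment is taken as related (8.1.1). The planned ORR sensitivity analyses (per-protocol and investigator-assessed) do not test undated therapy.

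**Working it through.** **1. Who has no cut-off under the present text**

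| Start date of documented later therapy | Rule that applies | BOR cut-off? |
|---|---|---|
| Complete | 4.9.1 window | Yes |
| Day missing, month and year known | 8.1.1 month-and-year comparison | Yes, to the month |
| Year missing | 8.1.1 no imputation, then 4.9.1 clause | No, unless a related record is dated |
| Fully missing | 8.1.1 no imputation, then 4.9.1 clause | No, unless a related record is dated |

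**2. Who in the last two rows can change an endpoint**

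- Scheduled scans after later therapy exist only for HSCT and CAR-T patients.
- For ORR, the patient must have had no earlier CR or PR, so mainly SD or NE, and must have a first central CR or PR after the procedure.
- For the CR rate, a PR that becomes CR after the procedure also counts.
- CAR-T is anticancer therapy by SAP 4.1.4. HSCT is covered if the term includes it. Protocol 9.7.2 includes it, but SAP 4.9.1 writes therapy/procedure in the sentence before the clause and only therapy in the clause itself.

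**3. The plan's own figures reproduce**

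Inputs are n=100, null 35%, alternative 55%, one-sided alpha 0.025 (SAP 3.1), and success at 45 or more of 100 (Table 7).

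- Type I error: P(Bin(100, 0.35) ≥ 45) = 0.0246.
- Power: P(Bin(100, 0.55) ≥ 45) = 0.9824, which agrees with the stated >98%.
- Exact lower bound: 35.03% at 45/100 and 34.08% at 44/100.
- At each of the other Table 7 sizes, too, one responder fewer puts the lower bound below 35% (34.29%, 34.14%, 34.88% and 34.20% at n=102, 105, 108 and 110).

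**4. Effect if one affected patient exists (an assumption; the documents give no number)**

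Shift in ORR or CR rate: 1/100 = 1.0 percentage point; 1/110 = 0.9.

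Type I error at a true 35% rate, with threshold c:
- Low end, where the patient counts as a responder whatever the true outcome: P(Bin(n−1, 0.35) ≥ c−1).
- High end, where one true non-responder is added to the count: P(Bin(n, 0.35) ≥ c−1).

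| n | c | As planned | One patient, low | One patient, high |
|---|---|---|---|---|
| 100 | 45 | 0.0246 | 0.0326 | 0.0389 |
| 102 | 46 | 0.0223 | 0.0296 | 0.0354 |
| 105 | 47 | 0.0244 | 0.0322 | 0.0382 |
| 108 | 49 | 0.0166 | 0.0221 | 0.0266 |
| 110 | 49 | 0.0241 | 0.0317 | 0.0375 |

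**5. Effect at the design rate of 55%**

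One added responder changes the result only if the true count is exactly one short. At n=100 that is P(Bin(100, 0.55) = 44) = 0.0071 or, with one patient known to be a non-responder, P(Bin(99, 0.55) = 44) = 0.0088. Across the Table 7 sizes the range is 0.4% to 0.9%. This must still be multiplied by the unknown chance that such a patient exists.

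**The case against.** **These dates are hard to lose.** The first new anticancer treatment is captured at EOT and at each 12-week follow-up visit (Schedule of Events). Transplant and CAR-T details, including conditioning, go into the eCRF (protocol 7.3), and start dates are collected (SAP 4.7.3). The 180-day safety windows after CAR-T, and after HSCT in responders (protocol 8.2, SAP 4.8.1.3), cannot be run without a procedure date. This stands, and it is why the likely count is zero or one.

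**The inflated type I error is conditional.** A reader might infer that the trial's type I error is 3.3–3.9%. The documents do not support that, because nothing in them says an affected patient will exist. If the chance of one were 5% (an illustrative assumption), type I error at n=100 would lie between 0.95×0.0246 + 0.05×0.0326 = 0.0250 and 0.95×0.0246 + 0.05×0.0389 = 0.0253.

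**Reach to HSCT depends on a reading.** If the clause covers therapies but not procedures, an undated transplant is unaddressed rather than declared not received. This also stands. The CAR-T route does not depend on it.

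**The protocol leaves detail to the SAP.** Protocol 9.7.1 has no missing-date rule, and protocol section 9 defers technical detail to the SAP. So the SAP may supply a convention. What it may not do is supply one that admits assessments the protocol's window excludes, and this clause can.

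**A conservative cap can do harm.** A cap at last dose + 30 days would discard valid scans. With the last dose at Week 6 and the next one held, the cap falls at (42+30)/7 = 10.3 weeks, before the Week 12 scan that protocol 7.3 requires even when dosing is delayed. An EOT scan may not exist either, since one within the previous 6 weeks suffices. Both points are accepted and shape the fix.

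**Conclusion.** The concern holds as a wrong rule with a narrow reach. The clause in SAP 4.9.1 can credit a response after later therapy to the study drug, against the window in protocol 9.7.1 and SAP 4.9, and SAP 8.1.1 does not close the gap when the date or its year is missing.

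The practical effect is probably nil or one patient: 1.0 percentage point on ORR or the CR rate at n=100. For the ORR test, type I error at n=100 would be 3.3–3.9% instead of 2.5% only if such a patient exists. At n=108 it could stay below 2.5% even then (2.2–2.7%). The CR rate has no hypothesis test, so there the effect is on a descriptive estimate.

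Two stronger readings are not supported. The sample size, power and Table 7 are not in error; all reproduce. Dates with only the day missing are not part of the defect: SAP 8.1.1 handles them by month and year. Treating every same-month scan as following the new therapy could remove EOT scans that protocol 4.2.3 places before new treatment.

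The conclusion assumes that a missing date alone triggers the clause, as its and/or wording says, and that no dated related record is used in its place.

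**What to change.** 1. In SAP 4.9.1, delete the and/or clause on missing start dates, so that only patients with no documented subsequent therapy are treated as having had none.
2. For documented therapy with a fully missing or year-missing start date, query the site. If the date stays unknown, use the earliest dated related record: conditioning, mobilization, the transplant or CAR-T procedure, or the visit that first reports the new therapy. That visit is only an upper bound on the start.
3. If there is no such record, count assessments up to the end of the Treatment Period: the EOT visit date, or the last scan on or before it if no EOT scan was done. Do not add a last dose + 30 days cap. State this in 8.1.1 as an exception to its no-imputation lines.
4. Say whether the term anticancer therapy includes HSCT, and use the same cut-off wherever SAP 4.9 relies on the start of subsequent therapy, including censoring for DOR, RFS and PFS.
5. Report how many patients are affected. Add two sensitivity analyses for them: one counting responses first read after the EOT visit as failures, and one counting them as successes (the current rule).
6. Leave the month-and-year comparison for day-missing dates as it is.

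**Cost.** A few sentences in 4.9.1 and 8.1.1 and a few lines of programming. Where step 3 applies, a genuine late response before an undated therapy is kept only in the sensitivity analysis. Step 3 also assumes that the therapy began after the EOT visit. Protocol 4.2.3 and 6.8.2 intend that order but do not guarantee it. If no patient is affected, no result changes.

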4.9.2 Duration of Response

Duration of response will be defined for patients with CR or PR only as the interval between the date of initial documentation of a response and the date of the first documented evidence of progressive disease based on independent radiographic assessment or death, whichever occurs first. Clinical progression at EOT/EOS without radiographic assessment could be considered as an event in a sensitivity analysis. Patients who have the event after the start of subsequent anticancer therapy/procedure, or are progression-free and alive at the time of

clinical cut-off, or have unknown status, will be censored at the last valid tumor assessment on or before the start of subsequent anticancer therapy/procedure or clinical cut-off time.

Patients with no post-baseline disease assessment will be censored on Day 1.

Duration of response will be estimated and displayed for the all-treated population using Kaplan-Meier methods (SAS® PROC LIFETEST). A Kaplan-Meier plot will be presented.

A sensitivity analysis of DOR will be conducted in which the DOR for patients undergo SCT will not be censored at SCT.

A sensitivity analysis of DOR per investigator assessments will also be conducted.

Subgroup analysis may be provided for disease subtype, disease stage, age group, sex, response to the first line and/or most recent line of prior systematic therapy (relapse: CR+PR vs. refractory: SD+PD vs. other: NE + missing), best response to camidanlumab tesirine (CR/PR), and other relevant variables.

4.9.3 Complete Response Rate

Complete response rate (CRR) will be defined as the proportion of patients with a best overall response of CR. The percentage of CRR with its 95% two-sided exact CI will be presented.

4.9.4 Time to Response

Time to response (TTR) is defined among patients who achieve either CR or PR as BOR before the start of subsequent anticancer therapy or procedure as the time from the first dose to the initial documented response. For this subset of patients, TTR will be summarized using descriptive statistics.

4.9.5 Relapse-free Survival

Relapse-free survival will be defined among CR patients as the time from the date of the first complete response until the date of the first disease relapse based on independent radiographic assessment (i.e., disease progression for CR patients) or death, whichever occurs first. The date of disease progression will be defined as the earliest date of disease progression based on central review. Clinical progression at EOT/EOS without radiographic assessment could be considered as an event in a sensitivity analysis. For patients who have the event after the start of subsequent anticancer therapy/procedure, or are progression-free and alive at the time of clinical cut-off, or have unknown status, censoring will be performed using the date of the last valid disease assessment on or before the start of subsequent anticancer therapy/procedure or clinical cut-off time.

Patients with no post-baseline disease assessment will be censored on Day 1.

RFS will be estimated and displayed for the all-treated population using Kaplan-Meier methods (SAS® PROC LIFETEST). A Kaplan-Meier plot will be presented.

A sensitivity analysis of RFS will be conducted in which RFS for patients undergo SCT will not be censored at SCT.

A sensitivity analysis of RPS per investigator assessments will also be conducted.

4.9.6 Progression-free Survival

Progression-free survival is defined as the interval between the date of the first dose and the date of the first disease progression based on independent radiographic assessment or death, whichever occurs first. Clinical progression at EOT/EOS without radiographic assessment could be considered as an event in a sensitivity analysis. Patients who have the event after the start of subsequent anticancer therapy/procedure, or who are progression-free and alive at the time of clinical cut-off, or have unknown status, will be censored at the time of their last valid disease assessment on or before the start of subsequent anticancer therapy/procedure or clinical cut-off.

Patients with no post-baseline disease assessment will be censored on Day 1.

PFS will be estimated and displayed for the all-treated population using Kaplan-Meier methods (SAS® PROC LIFETEST). A Kaplan-Meier plot will be presented.

A sensitivity analysis of PFS will be conducted in which the PFS for patients undergo SCT will not be censored at SCT.

A sensitivity analysis of PFS per investigator assessments will also be conducted.

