9.7.5 Progression-free Survival

The PFS will be defined among all-treated patients as the time from first dose of study drug until the first date of either disease progression or death due to any cause. The date of disease progression will be defined as the earliest date of disease progression based on central review. For patients whose disease has not progressed at the time of the analysis, censoring will be performed using the date of the last valid disease assessment. The data will be analyzed by the Kaplan-Meier method. The median PFS time and 95% CI will be presented. Further details will be outlined in the SAP.

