4.8.1.2 Deaths

The following deaths summaries will be generated on the all-treated population.

- Number (%) of patients who died during the study and reasons for death
- Number (%) of patients who died within 30 days after the last dose of study drug (excluding those who died after taking any subsequent anticancer therapy/procedure) and reasons for death

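### The SAP's Day 1 censoring sentence for PFS has no exception for death, so a death before the first scan is both an event and a censoring

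*SAP*

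**What the plan says.** SAP 4.9.6 measures PFS from first dose to centrally reviewed progression or death, whichever is first, in the all-treated population by Kaplan-Meier. Its main censoring sentence names three groups: patients whose event follows subsequent anticancer therapy or a procedure, those "or who are progression-free and alive at the time of clinical cut-off", and those with unknown status. They are censored at the last valid assessment. A separate paragraph then states: "Patients with no post-baseline disease assessment will be censored on Day 1". The same sentence stands in SAP 4.9.2 (DOR) and 4.9.5 (RFS).

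Protocol 9.7.5 runs PFS "until the first date of either disease progression or death due to any cause". Its censoring condition, however, begins "For patients whose disease has not progressed at the time of the analysis" and does not mention death. The DOR section (Protocol 9.7.2) begins its condition "For patients who have not progressed or died at the time of the analysis", and the RFS section (9.7.4) does the same.

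On timing, Protocol 7.3 says "imaging will be performed 6 weeks and 12 weeks after C1D1", with the Week 6 scan allowed up to one week before C3D1. Additional assessments are permitted if clinically indicated.

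**The concern.** A patient who takes at least one dose, receives no new therapy and dies before any scan belongs to none of the three groups in the main censoring sentence, so the death is an event. The next paragraph censors the same patient on Day 1. No order of precedence is given, and two programmers could code the case differently.

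The error goes one way. Early deaths are the worst outcomes, and removing them from the risk set at time zero raises the whole curve. In a single-arm, open-label study this coding should be settled before such a death is seen in the data. Literal Day 1 censoring would also depart from the protocol's event definition, while SAP 3.3 declares no modification to the protocol's statistical section.

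**Working it through.** **1. Does another passage settle it?**

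| Place | What it says about death before any scan |
|---|---|
| SAP 4.9.6, event definition | Event |
| SAP 4.9.6, main censoring sentence | Not among the censored groups |
| SAP 4.9.6, Day 1 sentence | Censored on Day 1, no exception |
| SAP 4.9.6, firm sensitivity analyses (no censoring at SCT; investigator assessment) | Do not address it |
| SAP 4.9.6, optional sensitivity analysis | Concerns clinical progression without imaging, not death as such |
| SAP 8.1.1, missing data | Silent |
| Protocol 9.7.5, event definition | Event |
| Protocol 9.7.5, censoring condition | Literally censors any death without progression; defers details to the SAP |

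Nothing resolves the conflict.

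**2. Who is affected?** Only treated patients who die unscanned. With the first scheduled scan 5 to 6 weeks after first dose, that is roughly the window, shorter if an earlier scan is done.

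**3. How large is the effect on the literal reading?** The plan gives no PFS figure to reproduce, and neither an early death rate nor a PFS median. Both are therefore assumed:

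- q = fraction dying before the first scan at 1.4 months (Week 6)
- m = median PFS in months among the others, exponential after 1.4 months, so λ = ln 2/(m − 1.4)
- no other censoring

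Formulas:

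- PFS at 6 months, deaths censored on Day 1: exp(−4.6λ), where 4.6 = 6 − 1.4
- PFS at 6 months, deaths as events: (1 − q)·exp(−4.6λ)
- overstatement factor after the first scan: 1/(1 − q)
- median, deaths as events: 1.4 + ln(2(1 − q))/λ

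For m = 9, λ = 0.6931/7.6 = 0.0912 and exp(−4.6 × 0.0912) = 0.657. For m = 6, λ = 0.6931/4.6 = 0.1507 and the value is 0.500.

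| q (assumed) | Factor | 6-month PFS, m = 9: event vs Day 1 | Median, m = 9: event vs Day 1 | 6-month PFS, m = 6: event vs Day 1 | Median, m = 6: event vs Day 1 |
|---|---|---|---|---|---|
| 0 | 1.000 | no difference | no difference | no difference | no difference |
| 1% | 1.010 | 0.651 vs 0.657 | 8.9 vs 9.0 | 0.495 vs 0.500 | 5.9 vs 6.0 |
| 2% | 1.020 | 0.644 vs 0.657 | 8.8 vs 9.0 | 0.490 vs 0.500 | 5.9 vs 6.0 |
| 5% | 1.053 | 0.624 vs 0.657 | 8.4 vs 9.0 | 0.475 vs 0.500 | 5.7 vs 6.0 |
| 10% | 1.111 | 0.592 vs 0.657 | 7.8 vs 9.0 | 0.450 vs 0.500 | 5.3 vs 6.0 |

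The 10% row is only an outer bound; nothing in the documents supports it.

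**4. Cross-check.** A Kaplan-Meier calculation on 100 patients, with 5 deaths spread over weeks 1 to 5 and the rest exponential after Week 6, gives 6-week PFS of 95% with deaths as events against 100% with Day 1 censoring. Medians are 5.6 vs 6.0, 8.3 vs 9.0 and 11.1 vs 12.0 months for assumed medians of 6, 9 and 12. Direction and size agree with the closed form.

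**The case against.** The strongest reply is that the Day 1 sentence merely supplies a date. The sentence before it censors at the last valid assessment, and a patient with no post-baseline assessment has none to use. Read in sequence, the sentence covers patients already due for censoring and leaves death as an event. Its repetition under DOR and RFS, where every patient has a response assessment and it can apply to nobody, suggests copied boilerplate. This is probably the intent, and on it the effect is nil. But the SAP is what programmers work from, and its plain words cover every patient without an assessment.

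Other points also carry weight:

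- Protocol 7.3 expects imaging to confirm clinical progression, if clinically indicated, so some patients who die early will have been scanned. It also includes a clinical examination in the assessment, so fewer patients may lack any assessment than lack a scan.
- The optional sensitivity analysis could capture a patient with clinical progression before death. It is not a commitment and does not reach other early deaths.
- Protocol 9.7.5 states the event correctly and defers to the SAP, whose main sentence requires patients to be alive. Changing it is a protocol amendment under Protocol 11.7, which this wording alone would hardly justify.
- The sizes above rest on assumed inputs.

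These points limit the consequence. They do not supply the missing exception.

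**Conclusion.** The concern holds. SAP 4.9.6 is contradictory on a literal reading and ambiguous on the kindest one, and the literal coding is wrong in the drug's favour. It cannot be said that the sponsor will code it that way.

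The size depends on how many patients die unscanned. It is zero if none do, or on the fallback reading. At an assumed 1% to 2%, with an assumed 9-month median, it is 0.1 to 0.2 month of median PFS and 0.6 to 1.3 percentage points at 6 months; at 5% it is about 0.6 month and 3.3 points.

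No primary conclusion is at risk. PFS is secondary, with no test or power attached. For ORR, SAP 4.9.1 says "all other patients (including those with missing response information) will be counted as failures". OS (SAP 4.9.7) keeps the deaths, and SAP 4.8.1.2 tabulates them: "Number (%) of patients who died during the study and reasons for death". It should be fixed because the correction is cheap and the bias has a known direction.

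**What to change.** In SAP 4.9.6, replace the Day 1 sentence with wording such as: *A patient without any post-baseline assessment is censored on Day 1, except that a death before any subsequent anticancer therapy and by the clinical cut-off is a PFS event on the date of death.* This keeps the existing censoring at new therapy and cut-off and changes only the disputed case. Make it before the database snapshot.

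In Protocol 9.7.5, extend the censoring condition to patients who have neither progressed nor died, to match 9.7.2 and 9.7.4. This can wait for the next amendment, provided the SAP is clear.

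Deleting the Day 1 sentence from SAP 4.9.2 and 4.9.5 is optional tidying and alters no estimate.

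The cost is one clause in each document and no new data. The PFS estimate may become slightly less favourable.
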